4.1 Primary Endpoint

Time to all hospital episodes (Emergency Room or patient request for OPD) related to treatment for atrial arrhythmia.

4.2 Secondary Endpoints:

1. Time to death or stroke from any cause.
2. Any complications caused by the procedure (pericardial effusion, bleeding >2 units, phrenic nerve palsy and other) or the anti-arrhythmic drug (GI disturbance, skin irritation and other).
3. All hospital episodes which result in a change in therapy for atrial arrhythmia.

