10.3 Adverse Event Intensity or Severity

The intensity or severity of each adverse event should be classified by the investigator according to the following guidelines:

Intensity	Description
Mild	Any event that results in minimal transient impairment of a body function and does not threaten damage to a body structure, and/or does not require intervention other than monitoring.

Moderate	Any event which results in moderate transient impairment of a body function or damage to a body structure, or which requires intervention.
Severe	Any event which is life threatening, results or could result in significant permanent impairment of a body function or damage to a body structure, requires significant and timely intervention to prevent permanent impairment of a body function or damage to a body structure, or which is intolerable or places the subject at immediate risk of harm.

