- g) Did you have any procedures whilst you were in hospital
If yes- what was it

ii) Have you had any of the following symptoms;

- a) racing heart beat lasting more than half an hour
if yes – <1/week or >1/week
- b) racing heart beat more than 5mins but less than half an hour
if yes – <1/week or >1/week
- c) Have you had any unexplained breathlessness, dizzy spells, chest pain, fainting attacks/weakness/confusion
if yes which-

iii) Do you think you the situation is bad enough that you need to change medication or have another procedure to help make you better? (yes/no)

**iv) Do you think you are having side effects or complications from your treatment?
(yes/no)**

v) If you have answered yes to any of the questions we recommend that you see your GP and discuss whether you need another appointment with your heart specialist. We will pass on the information from the phone call to your heart specialist and they may contact you directly if they are concerned about any of the answers you have given.

21 Appendix 2: AVATAR-AF Endpoint definitions

Symptoms of atrial fibrillation/tachycardia:	palpitations lasting >5min, transient dizziness or fainting, lethargy, shortness of breath on exertion, chest discomfort
• ECG documentation:	
• irregularly narrow QRS without p-waves lasting >30secs narrow QRS with A>V evident or 1:1 at >100bpm with sudden onset lasting >30sec or incessant at constant rate
Pericardial Effusion:	global echo-lucent space around myocardium >0.5cm maximally in diastole 
• SEVERE: pericardial drain inserted, sternotomy,• MODERATE: delayed discharge
Vascular Bleeding:	Bleeding visualised by haematoma or imaging associated with Hb drop of >2g/dl 
• SEVERE: Surgical intervention, transfusion required
Phrenic Nerve Palsy:	Reduced excursion of hemi-diaphragm on chest x-ray in inspiration and expiration more than 1day after procedure 
• SEVERE: exertional symptoms with CXR changes at >3mth• MODERATE: asymptomatic with CXR changes at >3mth
PV stenosis:	Evidence of >50 reduction in ostial PV diameter by any form of imaging. 
• SEVERE: exertional symptoms at >3mth• MODERATE: asymptomatic at >3mth
Drug Side Effect:	Symptoms that are well recognised with drug or stop after ceasing drug
Stroke:	logical symptoms/signs associated with MRI or CT evidence of neurological bleeding/ischaemia

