8.3. Secondary Endpoint Analysis

Time to death or stroke; time to procedural/drug-based complication and time to hospital episode resulting in change in therapy will be analysed using Kaplan-Meier statistics. Differences between treatment arms will be assessed using log-rank testing and proportional hazards models. Models containing one or more of the following co-variates may also be assessed if deemed necessary; site, weight, hypertension, number of anti-arrhythmic taken by patient prior to 1st intervention.

Secondary endpoint analysis will be carried out between AVATAR-AF Ablation and the Anti-Arrhythmic drug treatment arm in order to investigate the primary objective. The secondary objective will be assessed by testing AVATAR-AF Ablation against the Conventional Ablation arm.

Additional per-protocol analyses will be carried out in conjunction with the above.

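### The pooled complication test of AVATAR against drugs requires a measured finding for each named procedural item but sets no severity floor for a drug side effect, so mild drug symptoms could drive it

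*Protocol*

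**What the plan says.** Protocol 4.2 and 8.2 define secondary endpoint 2 as any complication caused by the procedure or by the drug. The examples given are "pericardial effusion, bleeding >2 units, phrenic nerve palsy and other) or the anti-arrhythmic drug (GI disturbance, skin irritation and other". SAP 7.2 lists pericardial effusion, vascular bleeding, phrenic nerve palsy, PV stenosis, drug side effects and an open 'other' as one variable. SAP 8.3 then states: "Time to death or stroke; time to procedural/drug-based complication and time to hospital episode resulting in change in therapy will be analysed using Kaplan-Meier statistics". Log-rank and Cox comparisons follow, and Tables 5.5.1 and 5.6.1 in SAP 8.7 apply them to AVATAR against anti-arrhythmic drugs.

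Protocol Appendix 2 gives the definitions:

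| Item | What must be shown | Severity grades given |
|---|---|---|
| Pericardial effusion | "global echo-lucent space around myocardium >0.5cm maximally in diastole" | severe, moderate |
| Vascular bleeding | "Bleeding visualised by haematoma or imaging associated with Hb drop of >2g/dl" | severe |
| Phrenic nerve palsy | "Reduced excursion of hemi-diaphragm on chest x-ray in inspiration and expiration more than 1day after procedure" | severe, moderate |
| PV stenosis | "Evidence of >50 reduction in ostial PV diameter by any form of imaging" | severe, moderate |
| Drug side effect | "Symptoms that are well recognised with drug or stop after ceasing drug" | none |

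Separately, Protocol 10.3 says "The intensity or severity of each adverse event should be classified by the investigator according to the following guidelines", and Protocol 10.4 supplies a causality scale. Neither is mentioned in the definition or analysis of endpoint 2.

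**The concern.** Within one pooled test, the named procedural events count only after an imaging or laboratory finding, while a drug event can count on a symptom alone. In a time-to-first-event analysis, one episode of mild stomach upset weighs the same as a drained effusion.

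At stake is how the AVATAR-versus-drug comparison of harm is read. The test could show an excess of complications on drugs that consists mostly of mild symptoms, while the serious events are balanced or lie in the ablation arm. Nothing in SAP 8.3 would separate these cases.

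**Working it through.** **1. Does another provision already equalise the threshold?**

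- *Causation.* The endpoint text requires the procedure or drug to be the cause, and the second limb of the drug definition (the symptom stops on withdrawal) is a dechallenge test. The two limbs are joined by 'or', however, so a symptom that is merely recognised for the drug meets the definition. Appendix 2 also lists lethargy, transient dizziness and exertional breathlessness as AF symptoms. Where one of these is also recognised for the patient's drug, it can satisfy the first limb.
- *Adjudication.* Protocol 8.4 has an independent committee verify events against the protocol definitions, which are the unequal ones.
- *Tables.* SAP Table 5.4 lists type, cause and relation to treatment but has no severity column. Table 7.1 grades all adverse events, not this endpoint. Neither restricts the test. SAP 8.8 titles the corresponding plot as complications of the procedure, although the tested variable includes drug effects.

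The gap therefore remains open in the tested variable.

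**2. Which way do detection and exposure push?**

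- *Towards more drug events.* Treatment is un-blinded (Protocol 5.4). The telephone calls ask patients whether they think they have side effects or complications (Appendix 1). The visit schedule has no chest X-ray or PV imaging. Anti-arrhythmics stop 4 weeks after ablation (Protocol 6.1, 6.3), while the drug arm enters follow-up on them (6.2).
- *Towards more ablation events.* AVATAR patients have an echo, Hb check and groin survey at 6 hours (6.1), repeated after a redo (6.4). The schedule has no echocardiogram after screening for the drug arm.
- *Diluting.* Ablation patients take drugs up to week 4 and may restart them after week 12 with documented recurrence (8.3).

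The net direction cannot be settled from the text.

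**3. Illustration of size.** The plan gives no rate, power or event count for this endpoint, so there is no figure to reproduce.

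Inputs from the documents: 100 evaluable patients per arm and two-sided alpha 0.025 (Protocol 11.1). SAP 8.3 states no alpha for secondary endpoints, so applying 0.025 here is an assumption.

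Assumed inputs: threshold-level complications b, equal in both arms; extra mild drug symptoms s in the drug arm; and a fraction f of that symptom rate in the AVATAR arm.

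- p_drug = 1 − (1 − b)(1 − s); p_abl = 1 − (1 − b)(1 − f·s)
- HR = ln(1 − p_abl) / ln(1 − p_drug); events D = 100 × (p_abl + p_drug)
- Chance of a significant excess on drugs = Φ(½·√D·|ln HR| − 2.241)

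Example with b = 0.05, s = 0.10, f = 0: p_drug = 1 − 0.95 × 0.90 = 0.145 and p_abl = 0.05. HR = ln 0.95 / ln 0.855 = 0.327 and D = 19.5. Then ½·√19.5 × 1.117 − 2.241 = 0.224, and Φ(0.224) = 0.59.

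| b | f | s = 5% | 10% | 20% | 30% |
|---|---|---|---|---|---|
| 5% | 0 | 0.18 | 0.59 | 0.99 | about 1.00 |
| 5% | 0.5 | 0.05 | 0.12 | 0.31 | 0.54 |
| 10% | 0 | 0.10 | 0.35 | 0.90 | about 1.00 |
| 10% | 0.5 | 0.04 | 0.08 | 0.24 | 0.45 |

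If one severity rule removed the mild symptoms, both arms would return to b and the chance would be 0.025/2 = 0.0125. With D as low as 100 × (0.0975 + 0.05) = 14.75, the normal approximation is rough.

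**4. Can the pooled and severe results diverge?** Suppose 5% in AVATAR against 20% on drugs in total, of which 3% and 1% are severe. The pooled HR is ln 0.95 / ln 0.80 = 0.23, and the severe-only HR is ln 0.97 / ln 0.99 = 3.03. These rates are also assumed; the example shows only that such a reversal is possible.

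**The case against.** A reader might infer that the drug item has no causality condition, that milder procedural events never count, and that the endpoint is therefore biased against drugs. The documents do not support any of these.

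- Causation is in the endpoint wording, the committee adjudicates both parts, and one limb of the drug definition tests withdrawal. What remains is the 'or' and the missing link to Protocol 10.4.
- The procedural cut-offs are mainly diagnostic, not floors of clinical severity. An effusion above 0.5 cm counts without drainage or delayed discharge, asymptomatic phrenic palsy and PV stenosis count, and procedural 'other' has no threshold. The asymmetry is confined to the named items.
- The scheduled post-ablation checks can find silent events that nobody looks for in the drug arm.
- The trial compares strategies. Side effects over a year of drug therapy are a real harm of that strategy, so counting them is legitimate. This stands: the any-severity composite answers a valid question, but not the question of serious harm.
- SAP Tables 5.4 and 7.1 to 7.4 would let a careful reader see severe events by arm. That helps, but it does not change what the planned test measures.
- Replacing the endpoint with events graded moderate or worse by investigators would be debatable in an un-blinded trial, and could lose asymptomatic phrenic palsy, which is moderate in Appendix 2 but might be mild under 10.3. This is a good reason to add a restricted comparison and not to substitute one.

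**Conclusion.** The point holds as a risk. The definitions are unequal for the named items, they enter one pooled test of AVATAR against drugs, and no other provision restricts that test. The result may therefore reflect mild drug symptoms more than the balance of serious harm.

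The documents do not establish bias in a given direction. They contain no complication rates, and detection works in both directions. In the illustration, the chance of a significant excess on drugs when threshold-level complications are equal ranges from 0.04 to about 1.00. It depends almost entirely on how common mild drug symptoms are and how many occur in the AVATAR arm. The comparison of AVATAR with conventional ablation is largely unaffected, because both arms have the same definitions and similar drug exposure.

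This is a worthwhile, low-cost improvement to a secondary endpoint and does not touch the primary analysis.

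**What to change.** In SAP 7.2 and 8.3 and Protocol Appendix 2:

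1. Count a drug side effect only if it is judged caused by the drug: at least 'possible' on the Protocol 10.4 scale and confirmed by the adjudication committee. Being well recognised should not be enough.
2. Keep the any-severity composite and add a comparison restricted to moderate or severe complications under one rule in all arms. State which 'moderate' governs: the Appendix 2 grades for the named procedural items, and the 10.3 scale for drug and other events. Asymptomatic phrenic palsy and PV stenosis are then retained.
3. Report procedure-related and drug-related components separately by arm and severity. State that no conclusion on comparative harm will rest on the any-severity composite alone.

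While editing, reconcile the bleeding criterion, which is given in units in Protocol 4.2 and SAP 7.2 but as an Hb drop in Appendix 2. Also say how arrhythmia-related events are graded, since Protocol 10.1 routes the non-serious ones to endpoint reporting instead of adverse event reporting.

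The cost is wording and some extra analysis. Severity and causality are already classified for adverse events, so no new data are needed. The downside is fewer events, and so less precision, in the restricted comparison.

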v1.1	24MAR2018	
Section 3.2 – Secondary Objective: Text changed from “...performed as a daycare has a comparable safety and efficacy profile to the conventional approach.” to “...performed as a daycare is less effective than the conventional approach.” to reflect update to Protocol v6.1
 
Section 5.5 – Sample Size: The alpha value assigned due to the Bonferroni Correction has been updated from 0.017 to 0.025 to as the trial is only analysing two pairs of treatments.
 
Section 5.5 – Sample Size: Number of events corrected from 97 to 103 (calculation not affected).Section 5.6 – Time and Events: Updated to reflect protocol update (± 3 days changed to ± 7)
 
Section 5.7 - Randomisation: Updated to reflect protocol update (± 3 days changed to ± 7)
 
Section 6 – Analysis Set: Additional text added to include for proposed per-protocol analyses.
 
Section 8.2 – Primary Analysis: The alpha has been updated to 0.025 due to the Bonferroni Correction alteration as above.
 
Section 8.2 – Primary Analysis: Additional text added to clarify analysis is to be carried out as per primary (AVATAR vs Anti-Arrhythmics) and secondary (AVATAR vs Conventional) objectives.
 
Section 8.2 – Primary Analysis: Additional text added to allow for per protocol analyses.
 
Section 8.3 – Secondary Analyses: see above edits for Primary Analysis
 
Section 8.4 – Safety Analyses: see above edits for Primary Analysis

3. Study Objectives

3.1. Primary Objectives

To determine if antral AF ablation without electrophysiological confirmation of PV isolation is more effective than anti-arrhythmic agents at achieving freedom from hospital based treatment.

3.2. Secondary Objectives

To determine if antral AF ablation without electrophysiological confirmation of PV isolation performed as a daycare is less effective than the conventional approach.

4. Study Endpoints

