Such a proposal may be controversial but its justification rests on whether symptom control or stroke prevention is the goal of AF ablation. Currently all guidelines indicate that symptoms are the only indication and yet 'any detectable AF' is used to assess procedures and it has become a 'sacred cow' that is rarely challenged.^{3,4,12-14} Cost-effectiveness studies on paroxysmal AF ablation, which have excluded any putative stroke or mortality benefits suggest incremental cost-effectiveness ratio of ablation versus medical therapy was \$51 431 per quality-adjusted life-year.¹⁸ This is still a considerable increase particularly as population studies suggest that the burden of AF is increasing with the aging population. Changing the definition of a successful ablation to the prospect of avoiding hospital episodes may enable the reduction of absolute costs of the procedure which would have a significantly beneficial effect on the cost effectiveness calculations. Review of our internal data suggests using the Advance™ Cryoballoon (Medtronic,Minneapolis) produces PV isolation >80% of veins without the need for additional ablation which requires PV mapping catheters. If the procedure is done without PV mapping, there are multiple cost savings PV mapping catheter, EP recording equipment and specialist staff. This would also shorten the procedure and may enable most patients to be completed as a day case which would be a cost saving through reduced bed occupancy. One series has suggested that nearly 90% of patient can already be discharged safely as a daycare.¹⁹ Our annual audits would support this view in that most complications (pericardial effusion, femoral bleeding, urinary retention, phrenic nerve injury) occur within three hours of the end of the procedure. The rest do not present during the overnight stay (atrio-oesophageal fistula, pulmonary vein stenosis, delayed tamponade). Simply changing the definition of success may enable all of these cost-savings to be made without compromising outcome to the patient.

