5.1. Introduction

Developments in paroxysmal AF ablation have been monitored against the definition of any detected 30seconds of AF, which is not necessarily measure of symptom control. Hospital episodes are an objective and well established endpoint throughout the healthcare system and are more reflective of the patient's expectations. The increasing population burden of AF will need more cost effective approaches to treatment of symptoms. It is not known whether current approaches to antral pulmonary vein ablation still necessitates pulmonary vein mapping, which is a major source of to cost and complexity.

The proposed study is based on the following observations:

- i) AF ablation is well established as the most effective method for preventing recurrence.
- ii) Current methods for AF ablation are costly and complex with only a minority of the AF population having access to such procedure.

- iii) The Advance Cryoballoon is effective at producing antral PV ablation.
- iv) AF ablation has not been compared against anti-arrhythmic agents with the primary goal of reducing hospital episodes.

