5.5. Sample Size

In this time-to-event study of hospital episodes, required sample numbers have been estimated using the log-rank test under the Freedman method based on the occurrence of first event during the 12-month follow-up period. The null hypothesis is that there is no difference in the distributions. Adopting a conservative approach, an initial two-sided alpha of 0.05 is chosen, given the need to allow for the inherent multiple testing between the three arms of the study, the conservative Bonferroni correction is applied and the alpha value used in the power calculations is reduced to 0.025.

Estimating the proportion experiencing a hospital episode in the follow-up period in the anti-arrhythmic arm as 0.63 and the corresponding proportion in the AVATAR ablation arm as 0.40, assuming the occurrence of 103 events, with 100 evaluable patients in each of the two treatment arms yields a power of 0.80. A similar power is obtained for the comparison of the AVATAR ablation arm (0.40) and the conventional AF ablation arm (0.20).

A sensitivity analysis indicates that these sample size estimates are reasonable. It is anticipated that the loss to follow-up will be small, approximately 7%. Consequently, 321 patients will be randomised in a 1:1:1 manner to a treatment strategy of either AVATAR protocol ablation, anti-arrhythmic therapy or conventional AF ablation and followed-up for 1 year.

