8.2. Primary Endpoint Analysis

Failure is counted when a patient experiences any hospital episode related to treatment for atrial arrhythmia. Time to failure will be taken as the time from 1st Intervention to the time of event.

Data will be analysed using the intention-to-treat principle and a p-value of 0.025 or less will be considered significant. Primary outcome will be analysed using Kaplan-Meier statistics and differences between treatment arms will be assessed using log-rank testing and proportional hazards models. Models containing one or more of the following covariates may also be assessed if deemed necessary; site, weight, hypertension, number of anti-arrhythmic taken by patient prior to 1st intervention.

Primary endpoint analysis will be carried out between AVATAR-AF Ablation and the Anti-Arrhythmic drug treatment arm in order to investigate the primary objective. The secondary objective will be assessed by testing AVATAR-AF Ablation against the Conventional Ablation arm.

An additional per-protocol analysis will be carried out in conjunction with the above.

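### The SAP tests both primary-endpoint comparisons at two-sided 0.025 but reports 95% confidence intervals, and Protocol 11.2 still sets 0.05

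*SAP*

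**What the plan says.** - **Level.** SAP 5.5 states that "an initial two-sided alpha of 0.05 is chosen". After a Bonferroni correction for multiple testing, "the alpha value used in the power calculations is reduced to 0.025". SAP 8.2 carries 0.025 into the primary-endpoint analysis as the significance threshold.
- **Tests.** SAP 5.5: "The null hypothesis is that there is no difference in the distributions". SAP 8.2: "differences between treatment arms will be assessed using log-rank testing and proportional hazards models".
- **Comparisons.** AVATAR v anti-arrhythmic drugs addresses the primary objective. For the other, "The secondary objective will be assessed by testing AVATAR-AF Ablation against the Conventional Ablation arm". SAP 3.2 words that objective as whether the unmapped procedure "performed as a daycare is less effective than the conventional approach".
- **Reporting shell.** SAP 8.7, Table 4.3 is to be produced once for each comparison (4.3.1 and 4.3.2). Each gives a hazard ratio, a two-sided p-value and a 95% confidence interval in one row.
- **Protocol.** Section 11.1 uses 0.025 for power. Section 11.2 sets significance at 0.05.
- **Not stated.** Neither document gives a non-inferiority or equivalence margin, or says how a non-significant AVATAR v conventional result is to be read.

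**The concern.** A 95% interval corresponds to a two-sided test at 0.05. Under the SAP's rule the corresponding interval is 97.5%. The Table 4.3 row can therefore contradict itself, with an interval clear of 1 and a p-value that the SAP calls non-significant. A reader who goes by the interval applies 0.05 to each of two comparisons, which undoes the Bonferroni correction. Protocol 11.2 gives that reader a text to cite, so the level in force is not settled by the two documents together.

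The interval matters most for AVATAR v conventional. There, a non-significant test says little by itself, and the interval is what shows how large a deficit remains possible.

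**Working it through.** **Inputs.** SAP 5.5: 12-month failure 0.63 (drugs), 0.40 (AVATAR) and 0.20 (conventional); 100 evaluable patients per arm; 103 events for AVATAR v drugs; Freedman method. Two-sided 0.025 gives z = 2.2414, and two-sided 0.05 gives z = 1.9600. The event count for AVATAR v conventional is not stated; it follows as 100 × (0.40 + 0.20) = 60.

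**Step 1: the plan's own figure.** For AVATAR v conventional, HR = ln(0.60)/ln(0.80) = 2.29 (inverse 0.437). Freedman power = Φ(√60 × (1 − 0.437)/(1 + 0.437) − 2.2414) = 0.787. Schoenfeld's formula gives 0.833 and a two-proportion test 0.807. The SAP's claim of power similar to 0.80 is reproduced at two-sided 0.025.

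**Step 2: which interval matches.** SAP 5.5 makes the starting alpha two-sided, and the p-value in the Table 4.3 shell is two-sided. A two-sided test at 0.025 pairs with a 1 − 0.025 = 97.5% interval.

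**Step 3: where test and interval disagree.** With 1:1 allocation the standard error of log HR is about 2/√events. The interval excludes 1 once the observed HR passes exp(z × 2/√events).

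- 60 events (AVATAR v conventional): 95% limit exp(1.9600 × 0.2582) = 1.66; 97.5% limit exp(2.2414 × 0.2582) = 1.78. The two disagree for HR 1.66 to 1.78, or 0.56 to 0.60.
- 103 events (AVATAR v drugs): exp(1.9600 × 0.1971) = 1.47; exp(2.2414 × 0.1971) = 1.56. The two disagree for HR 1.47 to 1.56, or 0.64 to 0.68.

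**Step 4: how often.** The chance that p falls between 0.025 and 0.05 is the power at 0.05 minus the power at 0.025.

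- No true difference: 0.05 − 0.025 = 2.5% per comparison.
- Planned effect, AVATAR v conventional (Freedman): 0.859 − 0.787 = 7.2%.
- Planned effect, AVATAR v drugs (Freedman, 103 events): 0.903 − 0.846 = 5.7%.

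**Step 5: what a null result would leave open.** Suppose the observed HR is 1.0 with 100 patients per arm. The event count then depends on the common failure risk, so a range is shown.

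| Risk in both arms | Events | 95% upper limit | 97.5% upper limit | AVATAR risk at the 97.5% limit |
|---|---|---|---|---|
| 20% | 40 | 1.86 | 2.03 | 1 − 0.80^2.03 = 36% |
| 30% | 60 | 1.66 | 1.78 | 1 − 0.70^1.78 = 47% |
| 40% | 80 | 1.55 | 1.65 | 1 − 0.60^1.65 = 57% |

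The design HR of 2.29 would be excluded in every row. A deficit of about 16 to 17 points would not. Seen from the other side, if the true risks were 20% v 30% (HR 1.60, 50 events), Schoenfeld power at two-sided 0.025 is 0.28, so the test would be non-significant about 72% of the time.

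**The case against.** **The mismatch is narrow and may be only a template.** The Table 4.3 shell looks like default software output, and nominal 95% intervals beside an adjusted alpha can be acceptable if labelled so. The band of disagreement is small (Step 3). This stands as to size. But the shell carries no such label, and it is the only place in the SAP that fixes the interval level.

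**95% might be right.** It would match if 0.025 were one-sided, or if Protocol 11.2 governed. The first reading conflicts with SAP 5.5 and with the two-sided p-value in the shell. The second shows why the protocol and SAP have to be reconciled before the interval level is settled.

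**A stronger reading is tempting.** Both documents ask whether mapping is needed (SAP 5.1: "It is not known whether current approaches to antral pulmonary vein ablation still necessitates pulmonary vein mapping"), and Protocol 1.1 hopes that a new definition of success "may enable all of these cost-savings to be made without compromising outcome to the patient". A reader might infer that the plan means a null result to justify dropping mapping, and that it is therefore a non-inferiority trial analysed with the wrong test. The documents do not support this:

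- The current objective asks whether AVATAR is less effective, and a difference test answers that question.
- The SAP change log records that an objective about a comparable profile was replaced.
- The sample size assumes that AVATAR does worse, 40% v 20%.
- The study hypothesis and primary objective compare AVATAR with drugs.
- Nowhere is a non-significant result said to show equivalence.

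What remains is that no rule for reading a null result is written down. That is a gap in detail, not a contradiction.

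**Conclusion.** The interval level is wrong as written for the SAP's own test, in both Table 4.3.1 and Table 4.3.2, and Protocol 11.2 conflicts with SAP 8.2 on the significance level. The effect is confined to results with p between 0.025 and 0.05. That is about 6% to 7% of trials under the planned effects by the Freedman formula, and 2.5% per comparison under no difference. These figures assume proportional hazards, equal allocation, the planned event counts and the usual large-sample standard error. The log-rank p-value will track the Cox p-value closely but not exactly.

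For AVATAR v conventional, objective and test agree. The limit is one of precision: the comparison can detect a doubling of failure from 20% to 40%, but cannot by itself show that the two procedures perform alike. The case for a sentence on interpretation rests on that imprecision, not on any intention shown in the plan.

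**What to change.** 1. Reconcile Protocol 11.2 with SAP 8.2 at 0.025, and state in SAP 8.2 that the level is two-sided and applies to each of the two comparisons.
2. Change the interval in Tables 4.3.1 and 4.3.2 to 97.5%. The Cox shells for the secondary endpoints (Tables 5.3, 5.6 and 5.9) also print 95%, while SAP 8.3 states no level, so settle those at the same time.
3. In SAP 8.2, base the reading of AVATAR v conventional on the hazard ratio with its 97.5% interval, and add that a non-significant test will not be reported as equivalence. No margin and no extra patients are needed.

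The cost is a wording change in each document and a column heading in the tables. Intervals become 2.2414/1.9600 = 1.14 times as wide on the log scale. The sentence on interpretation commits the authors to a more restrained conclusion if the result is null, so it should be in place before the results by arm are known.
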